6.7 Subject Withdrawal

Individual subjects may withdraw their consent to participate in the study at any time. Also, an Investigator may discontinue a subject's participation in the study at any time to protect the safety, rights, or welfare of the subject.

Subjects missing follow-up visits will not be considered lost to follow-up (LFU) until adequate attempts to contact the subject have been made.

7 CLINICAL STUDY TREATMENTS AND FOLLOW-UP VISITS

7.1 Informed Consent

It is the responsibility of the Investigator to give each subject full and adequate verbal and written information regarding all aspects of the study procedure, device, and associated risks. A signed informed consent form (ICF) must be obtained from the subject before any study procedures not considered standard of care (SOC) for an AF ablation are undertaken. The informed consent form must be signed by the subject and witnessed by the Investigator (or designee). The original signed consent is filed in the subject's study records with one copy placed in the subject's medical notes and one copy provided to the subject.

7.2 Subject Screening and Baseline

The following information should be acquired to verify eligibility in the clinical study:

- Subject demographics
- Medical history review including:
 - Procedural data of the previous AF ablation(s) including date(s), ablation strategy (PVI, PVI plus, etc.) and advanced mapping systems used, if any
 - Current AADs
 - Date of most recent direct current cardioversion (DCCV) with duration of sinus rhythm following the cardioversion
- Review of all inclusion/exclusion criteria to confirm subject eligibility
- Cardiovascular Exam

7.2.1 Mapping and Ablation

The objective of this clinical study is to evaluate the performance and efficiency of the AcQMap System when mapping and imaging the left and right atria during retreatment procedures for recurrent atrial fibrillation. Therefore, the utilization of devices for 3D anatomic reconstruction, navigation, and electrical mapping will be limited to the AcQMap System. Ablation energies for PVI may include RF, cryo, or laser. Ablation strategies to create pulmonary vein isolation is at the discretion of the investigator and may include antral ablations, wide area circumferential ablation (WACA), or “single shot” therapy. Radio frequency (RF) ablation catheters utilized during the procedure must be limited to those compatible with the AcQMap System. All PVI ablation strategies and catheter types shall be recorded on the procedure eCRF.

Refer to the Instructions for Use and Training Materials for a thorough description of the AcQMap preparation and delivery into the left atrium.

7.2.2 Procedure Data Collection

Collection of data generated during the procedure should include:

- Recording of 12-lead ECG at procedure start
- Recording of 12-lead ECG for predominant atrial arrhythmia(s)
- Recording of 12-lead ECG at procedure completion
- Total procedure time (from first venous access to last cardiac catheter removed)
- Total ablation time for PVI and non-PVI ablations
- Total fluoroscopy time for the ablation procedure
- Recording of all DCCV used during the procedure
- Recording of all IV cardiac medications infused during the procedure
- All alterations to ablation strategies due to esophageal proximity

7.3 Follow-Up Procedures

Screening, procedure, and follow-up visits are outlined in Table 2.

7.3.1 Hospital Discharge

Subjects should be monitored with telemetry prior to hospital discharge for the documentation of recurrence of any atrial arrhythmias. A recurrence prior to discharge **should not** be considered an adverse event unless it delays the discharge.

The following evaluations should be completed prior to discharge:

- Evaluation of femoral access sites
- AADs at discharge
- Evaluation and recording of adverse events
- 12-lead electrocardiogram

7.3.2 Visits at Three, Six and Twelve Months

The following evaluations will be performed during each clinic follow-up visit. Data will be recorded on the Follow-Up eCRFs.

- Arrhythmia recurrence/treatment since last visit
- AAD use and changes since last visit
- DCCV history since last visit
- 12-lead electrocardiogram
- 48-hour continuous monitor (may include Holter recording, BardyDx CAM or equivalent)

7.4 Recurrence of Atrial Fibrillation/Atrial Flutter/Atrial Tachycardia

Occurrences of symptomatic AF or other tachyarrhythmias during the first 90 days post-ablation (blanking period) may be transient in nature and not associated with the long-term effectiveness of the ablation treatment. However, prolonged AF should be treated as soon as possible to maintain SR during the remodeling period. Treatment should follow the Investigator's SOC for arrhythmia recurrence, which may include a DCCV and/or AAD administration. If the Investigator elects to repeat an ablation, a 48-hour continuous ECG monitor will be worn within two weeks and no later than 3 days prior to the procedure to document the presenting rhythm. The AcQMap System will be used during the procedure. Procedure and discharge data will be collected as part of RECOVER AF. There will be no adjustments to the scheduled follow-up periods and the study will be completed at 12-months post RECOVER AF index procedure.

Table 2: Schedule of Events

	Screening & Baseline	Procedure	Discharge	3-month (± 14 days)	6-month (± 30 days)	12-Month (± 30 days)	Retreatment Visit (if medically necessary)
CIP Informed Consent	X						
Medical History	X						
Arrhythmia Management Assessment				X	X	X	X
Cardiovascular Exam	X		X				X
AAD Medications	X	X	X	X	X	X	X
Procedure Data		X					X
Adverse Events		X	X				X
12-lead ECG		X	X	X	X	X	X
Continuous 48-hr ECG monitor				X	X	X	X (prior to retreatment)

8 STATISTICAL METHODS

Analysis of all data generated by the clinical study will be reported with descriptive statistics. There are no hypotheses established for the study therefore, the study sample size has not been established for power.

9 ADVERSE EVENTS

The safety outcome measure for this post-market study is a recording of all device and procedure related safety events through twenty-four (24)-hours post-ablation. Any event that occurs through twenty-four (24)-hours post-ablation is considered an AE and will be recorded on an Adverse Event eCRF. Any medical conditions, problems, signs, symptoms, or findings occurring prior to the AcQMap ablation procedure are to be considered as pre-existing conditions. The investigator has the responsibility of classifying any event as related to a component of the AcQMap System or the ablation procedure.

Serious Adverse Events (SAEs)

A Serious Adverse Event is any adverse event that:¹⁷

- led to death
- led to serious deterioration in the health of the subject, that either resulted in:
 - a life-threatening illness or injury, or
 - a permanent impairment of a body structure or a body function, or
 - in-patient or prolonged hospitalization, or
 - medical or surgical intervention to prevent life-threatening illness or injury or permanent impairment to a body structure or a body function
- led to congenital anomaly or birth defect

Reports relating to the subject's subsequent medical course following an SAE must be submitted to the Sponsor until the event has subsided or, in the event of permanent impairment, until the event has stabilized, and the overall clinical outcome has been ascertained.

¹⁷ EN ISO 14155:2011 section 3.37

Adverse Device Effects (ADEs)

Adverse Device Effects (ADEs) are a subset of AEs. The ADEs are only those AEs caused by, or related to the device, including any AE resulting from insufficiencies or inadequacies in the instructions for use, the System components, or any product malfunction, including any event that is a result of a user error or intentional misuse.

With any procedure or treatment, there are known possible risks and complications. A list of known or anticipated AEs for the AcQMap System is found in the CIP/protocol, Instructions for Use (IFU) and OM.

Unanticipated Adverse Device Effects (UADEs)

Investigators are required to submit a report to the Sponsor as soon as possible of any suspected Unanticipated Adverse Device Effect (UADE) occurring during an investigation, but no later than five (5) business days after the Investigator first learns of the effect.

When an Investigator suspects an event meets the definition for a UADE, then the event, date of onset, seriousness, severity, duration, treatment, outcome, and relationship to device will be recorded on the Adverse Event CRF. Additionally, reports must be provided to the reviewing Ethics Committee (EC) per national and local requirements.

The Sponsor/manufacturer must then conduct an evaluation of the suspected UADE and report the results of the findings to the Notified Body and to all reviewing ECs and participating Investigators within five (5) business days after first receiving notice of the effect. Thereafter, the Sponsor shall submit such additional reports concerning the effect as the Notified Body requests.

9.1 Adverse Event Reporting

The Investigator is responsible for reporting all procedure and device related AEs that occur within the first twenty-four (24) hours of the ablation procedure. Initial reporting will be with the Adverse Event eCRF; however, additional information may be required by the Sponsor or any regulatory authority. The Investigator should report any SAEs, SADEs, or UADEs to the Sponsor as soon as possible after becoming aware of the event, but no later than five (5) business days after receiving knowledge of the event occurrence. All SAEs, SADEs, and UADEs will be documented on the Adverse Event eCRF along with an explanation of any medical treatment administered. Documentation should include the time of onset, complete description of the event, severity, duration, actions taken, and outcome.

9.2 Event Relationship to the Device

The Investigator should provide information regarding the relationship of the event to the procedure and/or the AcQMap System or any of the components (AcQMap Catheter, AcQGuide Sheath, or Patient Electrode Kit). The device relationships are defined in the table below:

Table 3: AE Relationships

Not Related	The cause of the AE is known and is not related to any aspect of the mapping and imaging portion of the ablation procedure.
Possibly Related	There is a reasonable possibility that the event may be related to the mapping and imaging portion of the ablation procedure. The AE has a timely relationship to the study procedure(s); however, it follows no known pattern of response and an alternative cause seems more likely or there is significant uncertainty.
Probably Related	It is probable that the event is related to the mapping and imaging portion of the ablation procedure. The AE has a timely relationship to the study procedure(s) and follows a known pattern of response , but a potential alternative cause may be present.
Definitely Related	The event is definitely related to the mapping and imaging portion of the ablation procedure. A related event has a strong temporal relationship and an alternative cause is unlikely.

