5.2 Clinical Study Design Justification

Previous clinical studies utilizing the AcQMap System in an ablation procedure for supraventricular tachycardias (SVTs) have initially demonstrated an acceptable safety profile when mapping and imaging cardiac chambers. The RECOVER AF study is a prospective, single-arm, multi-center, multi-national, non-randomized, post-market study designed to provide clinical data regarding the use of the AcQMap High Resolution Imaging and Mapping System during an atrial fibrillation retreatment ablation procedure. Recording of all Serious Adverse Events/Device Effects occurring during the first twenty-four (24) hours post-procedure will be used to assess the safety related to the AcQMap Catheter, AcQGuide Steerable Sheath, and the AcQMap System.

Since it is hypothesized the technology advances of dipole density mapping may better identify and more precisely direct lesion locations during atrial arrhythmia ablations, the study is additionally designed to record longer term (6- and 12-month) data on the effectiveness of the ablation procedure in the treatment of the arrhythmia. An analysis of treatment success (defined as freedom from atrial arrhythmias at 6- and 12-months), compared to literature based historical controls, may offer insight regarding the ability of the AcQMap System to effectively and accurately identify appropriate ablation targets.

Automatic, instantaneous, and simultaneous 3D display of the LA surface with associated charge densities may potentially shorten atrial arrhythmia ablation procedure time and provide an intuitive tool to rapidly identify and guide effective treatment.

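### Table 3 is meant to define relationship to the device but grades against an undefined phase of the procedure, so some device-caused events can be graded Not Related

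*Combined protocol and SAP*

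**What the plan says.** Section 9.2 asks the investigator how an event relates to the procedure and/or the AcQMap System or its components, and it lists the catheter, the AcQGuide sheath and the patient electrode kit. It then states: "The device relationships are defined in the table below".

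Table 3 has four grades:

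- Not Related sets two conditions: "The cause of the AE is known and is not related to any aspect of the mapping and imaging portion of the ablation procedure".
- The next grade up, Possibly Related, is worded: "There is a reasonable possibility that the event may be related to the mapping and imaging portion of the ablation procedure". This row also takes events whose attribution is significantly uncertain.
- Probably Related is worded: "It is probable that the event is related to the mapping and imaging portion of the ablation procedure".
- Definitely Related is worded: "The event is definitely related to the mapping and imaging portion of the ablation procedure".

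Section 9 uses a different basis: "The ADEs are only those AEs caused by, or related to the device". It counts malfunction and user error as device causes, and it makes the investigator assign each event to a System component or to the ablation procedure. Section 5.2 says that the serious events and device effects recorded in the first 24 hours "will be used to assess the safety related to the AcQMap Catheter, AcQGuide Steerable Sheath, and the AcQMap System".

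**The concern.** A relationship scale should refer to the thing being assessed. Here that is a device with several components, but the scale refers to a stage of the procedure. The two agree only if the device can cause harm only during that stage.

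Device- and procedure-related events through 24 hours are the study's safety outcome (sections 6.2.1 and 9), and section 13.2 allows the data to support a regulatory filing. If a known device cause can be graded Not Related under one section and be an ADE under another, the number of device-related events depends on which section the investigator follows. With up to 15 sites (section 6.4) and no definition of the stage, sites can differ.

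**Working it through.** No arithmetic is needed to establish the point, and the plan states no figure to reproduce. The check is a comparison of texts.

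**Step 1. What the grades refer to.** Four of four rows refer to the mapping and imaging portion. None of the four refers to the System, the catheter, the sheath or the electrode kit. The protocol does not define the portion, its start or its end.

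**Step 2. What the surrounding text requires.**

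| Place | Basis for attribution |
|---|---|
| 9.2, lead-in | Procedure and/or System or named component |
| 9.2, Table 3 | Phase of the procedure |
| 9, ADE definition | Device |
| 9, investigator's duty | Component, or ablation procedure |
| 5.2, safety purpose | Catheter, sheath and System |

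Table 3 is the only one of the five that uses a phase, and it is the only relationship scale given. The lead-in also asks about relationship to the procedure, but no scale for that appears.

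**Step 3. Is the device in use outside the phase?** Section 5.4.1 describes navigating catheters within the AcQMap image as a System function. Section 7.2.1 makes it the only such system allowed: "the utilization of devices for 3D anatomic reconstruction, navigation, and electrical mapping will be limited to the AcQMap System". Section 6.5 defines a completed procedure as one in which non-PV targets were both mapped and ablated using the System. Use of the device therefore extends into ablation. For the sheath the text is less clear. Section 5.4.3 describes placing it in the chamber so that the mapping catheter can be introduced and directed. That may count as part of mapping, and nothing is said about its withdrawal.

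**Step 4. Apply the rules to one case.** Suppose an injury during ablation is traced with confidence to an AcQMap navigation error.

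- Section 9: the device, or an error in using it, caused the event, so it is an ADE.
- Table 3, Not Related: the first condition, a known cause, is met. The second, no link to any aspect of mapping and imaging, is met if navigation during ablation lies outside the portion. The text does not settle this.
- Result: one event can be both an ADE and Not Related.

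**Step 5. What one regraded subject is worth.** Section 6.4 plans up to 100 treated subjects. If 100 is the denominator, one subject moved between related and not related changes the device-related percentage by 1/100 = 1 percentage point. The documents give no rate for device events inside or outside the phase, so the number of subjects affected cannot be derived.

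**The case against.** The strongest reply is that the rest of section 9 contains the problem.

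- Every event through 24 hours goes on an adverse event form whatever its grade, and the safety outcome covers procedure-related as well as device-related events. A navigation or sheath injury would normally stay in that outcome. This stands: events are not lost.
- Not Related requires a known cause, and doubtful cases go to Possibly Related. This narrows the exposure but does not remove it. The exposed events are those whose device cause is clear.
- Sections 9 and 9.2 already ask for attribution by component, so a careful investigator could grade by device despite the table. This is true, but another could follow the table. The sponsor's clinical representative evaluates events (section 9.5), and sponsor staff attend procedures and report malfunctions (section 9.4). Neither section gives a rule for correcting a grade.

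A reader might also infer several stronger things that the documents do not support:

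- *Sheath injuries in general grade as Not Related.* Using the sheath to deliver the mapping catheter is arguably an aspect of mapping. Only sheath events traced to some other stage are exposed.
- *No result for the sheath is possible.* Attribution by component is already required, and the eCRF is not available, so one cannot say that a field is missing.
- *Section 5.2 promises separate assessments.* It names the three items but does not say that they will be assessed separately.
- *Events caused by other equipment during mapping would be graded device-related.* The rows ask whether the event is related to the mapping and imaging portion, not merely whether it occurred during it.

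**Conclusion.** Wrong as written. Table 3 states a rule for device relationship that does not refer to the device, and it disagrees with its own lead-in, with section 9 and with section 5.2. That holds on the text alone.

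The practical effect is narrower: possible misattribution, and inconsistent grading between sites, among events that are recorded anyway. It rests on two readings: that investigators apply the table literally, and that at least some navigation during ablation falls outside the mapping and imaging portion. The second is plausible but not settled, because the portion is undefined.

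A reader might want to attach a number, or to conclude that the reported safety result will be materially biased in the device's favour. The documents support neither. They give no event rates, and any calculation would need assumed rates plus the assumption that every out-of-phase event is misgraded. The gap described here lets device-caused events be under-attributed, but neither its size nor the net direction across all grading can be shown.

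**What to change.** - In all four rows of Table 3, replace the reference to the mapping and imaging portion with: the AcQMap System or any of its components (AcQMap Catheter, AcQGuide Sheath, Patient Electrode Kit, Console/Workstation including navigation). Set no phase or time limit in the grades. A window such as first venous access to last removal would only exchange one phase limit for another, and could miss an electrode-kit effect that arises before access.
- Grade relationship to the ablation procedure separately, on the same four levels, since the lead-in asks for both. Allow an event to be graded on both scales.
- Report device-related events by the component that section 9 already requires the investigator to identify.

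The cost is an edit to one table and a small eCRF change. The device-related count may become slightly less favourable.

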9.3 Death Notice

When a site becomes aware of a subject's death, it should be reported to the Sponsor. Notification should be made to the reviewing EC per local requirements.

9.4 Device Complaint and Malfunction

Each clinical procedure will be attended by Acutus Medical personnel responsible for the proper use of the technology. If a malfunction occurs, the Sponsor representative will report the findings to the Clinical and Product Complaints departments. Evaluations of all complaints will follow Acutus Medical QAPs for complaint handling.

9.5 Adverse Event Analysis

All procedure and device related adverse events will be evaluated by a clinical representative for Acutus Medical. Reporting to convening ECs will follow local regulatory requirements.

10 RISK: BENEFIT ANALYSIS

10.1 Risks

The following adverse events are associated with electrophysiology mapping and ablation procedures:

- Adult Respiratory Distress Syndrome
- Air embolism
- Anemia
- Anesthesia reaction
- Aorto-right atrial fistula
- Arrhythmias
- Arteriovenous (AV) fistula
- AV or SA node damage
- Atrial esophageal fistula
- Cardiac perforation/tamponade
- Cardiac thromboembolism
- Cerebral infarct (hemorrhagic or thromboembolic)
- Chest pain/discomfort
- Complete heart block (transient or permanent)
- Congestive heart failure
- COPD exacerbation
- Coronary artery spasm/dissection
- Coronary artery thrombosis/occlusion
- Death
- Diaphragmatic paralysis
- Dislodgement of ICD/pacemaker leads
- Elevated cardiac enzymes
- Endocarditis
- Local hematomas/ecchymosis
- Major bleeding, requiring surgery or transfusion
- Myocardial infarction
- Obstruction, perforation or damage to the vascular system
- Pericardial effusion
- Pericarditis
- Phrenic nerve damage
- Pleural effusion
- Pneumonia
- Pneumothorax
- Pseudoaneurysm
- Pulmonary edema
- Pulmonary embolism
- Pulmonary hypertension
- Pulmonary vein dissection
- Pulmonary vein stenosis
- Pulmonary vein thrombosis
- Radiation injury
- Respiratory depression
- Seizure
- Skin burns
- ST segment elevation
- Temporary complete heart block

- Fever
- Fluid overload
- Heart failure/pump failure
- Hemothorax
- Infection/sepsis
- Thromboembolism
- Transient ischemic attack (TIA)
- Valvular damage/insufficiency
- Vasovagal reaction

10.2 Mitigation of Risks

Pre-clinical research and ongoing clinical studies have demonstrated that the system is safe for human use. All potential risks have been evaluated and mitigation strategies have been implemented to reduce potential risks to acceptable levels. Acutus Medical believes that the potential benefits of the system outweigh the potential risks.

